1.0 Background

- 1.1 Worldwide, nearly 1.3 million patients are diagnosed with and more than 600 000 patients die from colorectal cancer every year (Ferlay et al, 2013). Regorafenib is a novel oral multikinase inhibitor that blocks the activity of several protein kinases, including kinases involved in angiogenesis, oncogenesis and tumor microenvironment (Kies et al, 2010). Regorafenib was recently shown to provide a survival benefit in metastatic colorectal cancer patients who have progressed after all standard therapies (Grothey, et al). This led to its approval in September 2012 by the FDA for use in the United States. Despite the observed benefits in a patient population with no current standard, toxicities such as Palmar-plantar erythrodysesthesia syndrome (PPES) (which occurs early in the first 1-2 weeks) and fatigue have widely limited its use in the US. Multiple practices across the US have adopted, and despite the absence of supportive data, various dosing or interval scheduling including starting at lower doses and escalate as tolerated, every other week dosing intervals and other.

In this study, we propose to design a novel strategy to optimize the dose of regorafenib in patients with refractory mCRC to allow maintenance of the observed benefits while improving the tolerability profile. The proposed strategy, arm A (combining A1 and A2) consists of starting regorafenib at 80 mg/day for 1 week (week1), then if no significant drug-related toxicities escalate to 120 mg/ day for another week (week 2), then again if no significant related toxicities escalate to a total dose of 160 mg/day (week 3) followed by a week break (week 4 of cycle 1). If at the end of week 1, week 2 or week 3 toxicities are unacceptable as defined by the study, the decision will be to deescalate by 40 mg/day and there will be no further dose escalations. A comparative arm, arm B (combining B1 and B2) will include a standard dose/schedule regorafenib of a 160 mg/day starting on day 1 of cycle 1. The primary goal of this study is to compare the proportions of patients on each arm who complete 2 cycles of protocol treatment and initiate cycle 3. We will also assess other outcome and quality of life measures and toxicity profile with a focus on regorafenib related toxicities. We will also assess a potential strategy to reduce the severity of PPES. Additionally, we will perform limited PK analysis in both arms.

To explore a potential strategy to reduce the severity of PPES, Clobetasol 0.05% cream for first 12 weeks will be prophylactically applied to palms and soles of patients in arm A1 and (pre-emptive strategy). Patients in arm A2 and B2 will be treated per investigator discretion when they develop PPES (reactive strategy). All patients will be required to fill HFS14 quality of life questionnaire on C1D14, C2D1, C2D14, and C2D28 intervals.

1.2 QOL Tools

- 1.21 QOL is an important outcome and covariate in this trial because the treatments are expected to differ in terms of their symptom profiles and impact on patient well-being. Previous data has indicated that the most prevalent QOL issues with these patients are fatigue, pain, weight loss, and other symptoms, as well as more general aspects of QOL such as ability to enjoy life and contentedness in QOL (Odom et. al. 2010). We hypothesize that patients receiving regorafenib will experience greater deficits in QOL as reflected by scores on the HSF14, the BFI and the LASA. These questionnaires have specific application to this population.

The HSF14 has been specifically designed to capture changes in QOL related to PPES. Cronbach's alpha for this questionnaire is 0.93. It involves 14 questions

with three domains: hand, feet, and social. The final score for this questionnaire ranges from 2-100, where a higher score indicates greater QOL impairment (Sibaud et. al., 2011). For comparison to other QOL questionnaires, the HSF14 will be converted to a 0-100 scale, where a higher score indicates better QOL.

The Brief Fatigue Inventory (BFI), a 9-item questionnaire, has been validated as a short and comprehensive instrument to assess severity of fatigue and fatigue-related impairment in cancer patients. The reliability estimated with Cronbach's alpha ranges from 0.82 to 0.97. Recently, both the German version and the Japanese version of the BFI has been validated with test-reliability (mean scores of 0.93) and impairment (mean scores of 0.87) for the German version and reliability with Cronbach's alpha at 0.96 for the Japanese version. Minor differences were seen in the validation of the German version compared to the original version.

Linear Analogue Self Assessment (LASA) items have been validated as general measures of global QOL dimensional constructs in numerous settings (Grunberg et al., 1996; Gudex et al, 1996; Hyland et al., 1996; Srivatanakul, 1983; Wewers, 1990). A series of LASA items have been constructed and validated at Mayo Clinic for use in cancer patients (Bretscher et al, 1999). These items have been seen to be important prognostic factors for cancer patient survival and should be included as covariates in survival analysis (Sloan, JCO, 2012).

1.3 Correlative Research

1.31 Regorafenib clinical pharmacokinetics

Regorafenib and its metabolites M2 and M5 have been assessed pharmacokinetically in several phase I studies, both with regorafenib dosed 21 days on/7 days off (Mross K et al. 2012; Strumberg D et al. 2012; Sunakawa Y et al. 2014), and with continuous dosing (Kies MS et al. 2010; Finn RS et al. 2013). Based on safety, efficacy and PK analysis (higher exposure on dosing days), the final dose taken into phase III studies was 160 mg 21 days on/7 days off.

Regorafenib is moderately fast absorbed after oral administration with median t_{max} of 3 to 4 hours, and mean C_{max} of 2.5 mg/L. Steady-state is expected to occur within 7 days after first administration. The overall mean terminal half-life at steady state is 20-30 hours, with a $t_{max,ss}$ of 5 hrs. Mean $C_{max,ss}$ and $AUC_{(0-24)ss}$ with 160 mg dosing were 3.9 mg/L and 58.3 mg•h/L. In the dose escalation phase I studies, regorafenib PK at doses above 60 mg was less than dose proportional. Accumulation of regorafenib from day 1 to day 21 was consistent with linear pharmacokinetics (Mross K, et al .2012).

Regorafenib has 2 major active metabolites, M2 and M5. While both regorafenib and M2 have elimination half-lives of 20-30 hrs, the M5 active metabolite has a half-life of 60 hrs (range 40-100 hrs).

Regorafenib and its active metabolites have substantial variability in their plasma exposure – expressed as either the maximum concentration shortly after administration (C_{max}) or the area under the concentration-time curve (AUC) – after oral regorafenib administration. The coefficient in variation (standard

deviation/mean) of C_{\max} ranges from 61.9% to 173.5%, showing considerable interpatient variability in the absorption. This is not unexpected since regorafenib's absorption is influenced by the fat content in the diet (Section 15.15). Similarly, the AUC has substantial variability with the CVs ranging from 77.8 to 182.4%. This is also not unexpected since regorafenib undergoes enterohepatic recirculation, and is susceptible to a multitude of drug interactions since it is a CYP3A4 and UGT1A9 substrate (Section 15.15). Furthermore, within-patient variability is present such that an individual patient can have dose-to-dose variability in their pharmacokinetics.

No relationship was suggested between AUC or C_{\max} of regorafenib, M2 or M5 and adverse events in phase 1 trials, but it was suggested that an exposure of ≥ 60 mg daily of regorafenib was associated with greater efficacy (regorafenib IB).

1.32 Rationale for regorafenib pharmacokinetic studies

Regorafenib has clinical activity in CRC, but many patients discontinue treatment in the first 2 cycles due to adverse events (Grothey A et al. 2013). In the few phase I studies to date, small patient numbers underwent any PK evaluation at steady state beyond cycle 1, to understand a possible connection between toxicity and PK parameters.

Because this clinical trial seeks to optimize the regorafenib dose and overall exposure in patients with refractory mCRC, it is critical that we evaluate the pharmacokinetic parameters of regorafenib and its metabolites, and assess whether their PK variability is clinically relevant. To our knowledge, no large pharmacokinetic correlative studies – or those studies evaluating if plasma regorafenib concentrations are associated with its efficacy or toxicity – have been conducted to date.

Therefore, as detailed in Section 14.1, we have developed a clinic-friendly sampling schedule to collect the PK trough levels (C_{\min}) for the study drug and its metabolites, to maximize patient compliance. In the low dose (dose escalation) cohort, as the regorafenib dose is planned to be escalated weekly in cycle 1 from 80 to 120 to 160mg, trough levels will be collected on days 7, 14 and 21, when each regorafenib dose would be expected to reach steady state. These visits coincide with regular clinic visits for safety/toxicity evaluation. In cycle 2, PK will be collected on days 1 and 21. To be able to compare the low dose, escalating cohort with the standard dose cohort, similar time-points for PK analysis were chosen.

2.0 Goals

2.1 Primary

- 2.11 Evaluate the proportion of patients who complete 2 cycles of protocol treatment and initiate cycle 3 in arm A (pooled arm A1 and A2) and arm B (pooled arm B1 and B2).

2.2 Secondary

- 2.21 Evaluate outcome measures for efficacy in each arm including progression-free survival (PFS), time to progression (TTP), and overall survival (OS).
- 2.22 Compare between arms the cumulative dose and dose intensity received within the first two cycles.
- 2.23 Evaluate the proportion of patients in each arm that exhibit grade 3 Palmar-plantar erythrodysesthesia syndrome (PPES) and/or fatigue, and make comparisons between regorafenib dosing strategies and pre-emptive vs. reactive strategies to address PPES.
- 2.24 Compare QOL between treatment arms (regorafenib dosing strategies and pre-emptive vs. reactive PPES strategies) as measured by the HFS14, BFI, and LASA questionnaires.

2.3 Correlative Research

- 2.31 Evaluate and compare trough (C_{\min}) PK during the first 2 treatment cycles for regorafenib and active metabolites M2, M5 between the low dose (dose escalation) and the standard dose cohorts, and correlate with toxicity profile.
- 2.32 Evaluate the correlation between PK parameters and tumor response/stable disease after the first two cycles.
- 2.33 Evaluate the correlation between PK parameters and PFS and OS.
- 2.34 Evaluate if trough (C_{\min}) concentrations are associated with patient-specific factors (such as – but not limited to – age and concomitant medications).

3.0 Patient Eligibility

3.1 Inclusion Criteria

- 3.11 Age ≥ 18 years.
- 3.12 Histological or cytological documentation of adenocarcinoma of the colon or rectum.
- 3.13 Advanced or metastatic colorectal cancer with no curative options available and progression on previous standard therapy, including an EGFR inhibitor if KRAS wild-type.
- 3.14 Measurable or non-measurable disease as defined in Section 11.0.
- 3.15 ECOG Performance Status (PS) 0 or 1. (Form is available on the ACCRU web site <https://www accr u.org/accru/forms/NonProtocolSpecificForms/index.html>).
- 3.16 Life expectancy of ≥ 3 months.

- 3.17 The following laboratory values obtained ≤ 7 days prior to randomization.
- Absolute neutrophil count (ANC) $> 1500/\text{mm}^3$
 - Platelet count $> 100,000/\text{mm}^3$
 - Hemoglobin > 9.0 g/dL
 - Total bilirubin ≤ 1.5 x upper limit of normal (ULN)
 - Alanine aminotransferase (ALT) and aspartate amino-transferase (AST) ≤ 2.5 x ULN (≤ 5 x ULN for subjects with liver involvement of their cancer)
 - Serum creatinine ≤ 1.5 x ULN
 - INR/PTT ≤ 1.5 x ULN
- NOTE: Patients who are therapeutically treated with an agent such as warfarin or heparin will be allowed to participate provided that no prior evidence of underlying abnormality in coagulation parameters exists. Close monitoring of at least weekly evaluations will be performed until INR/PTT is stable based on a measurement that is pre-dose as defined by the local standard of care.
- Alkaline phosphatase limit ≤ 2.5 x ULN (≤ 5 x ULN for patients with liver involvement of their cancer)
- 3.18 Negative serum pregnancy test done ≤ 7 days prior to randomization, for women of childbearing potential only. NOTE: Post-menopausal women (defined as no menses for at least 1 year) and surgically sterilized women are not required to undergo a pregnancy test. The definition of adequate contraception will be based on the judgment of the investigator.
- 3.19a Ability to complete questionnaire(s) by themselves or with assistance.
- 3.19b Provide informed written consent.
- 3.19c Willing to return to enrolling institution for follow-up (during the Active Monitoring Phase of the study).
- 3.19d Willing to provide blood samples for correlative research and banking purposes (see Sections 6.0 and 14.0).
- 3.2 Exclusion Criteria
- 3.21 Prior treatment with regorafenib.
- 3.22 Major surgical procedure, open biopsy, or significant traumatic injury ≤ 28 days prior to randomization.
- 3.23 Congestive heart failure $>$ New York Heart Association (NYHA) class 2.
- 3.24 Unstable angina (angina symptoms at rest), new-onset angina (begun within the last 3 months) or myocardial infarction less than 6 months prior to randomization.
- 3.25 Cardiac arrhythmias requiring anti-arrhythmic therapy. Note: Pace makers, beta

blockers or digoxin are permitted.

- 3.26 Uncontrolled hypertension. (Systolic blood pressure > 140 mmHg or diastolic pressure > 90 mmHg despite optimal medical management).
- 3.27 History of or current pheochromocytoma.
- 3.28 Arterial or venous thrombotic or embolic events such as cerebrovascular accident (including transient ischemic attacks), deep vein thrombosis or pulmonary embolism ≤ 6 months prior to randomization.
- 3.29a Ongoing infection > grade 2 NCI-CTCAE version 4.0.
- 3.29b Known history of chronic hepatitis B or C.
- 3.29c Patients with seizure disorder requiring medication.
- 3.29d Symptomatic metastatic brain or meningeal tumors unless the patient is > 6 months from definitive therapy, has a negative imaging study within 4 weeks of randomization and is clinically stable with respect to the tumor at the time of randomization. Note: Patient must not be undergoing acute steroid therapy or taper (chronic steroid therapy is acceptable provided that the dose is stable for one month prior to and following screening radiographic studies).
- 3.29e History of organ allograft (including corneal transplant).
- 3.29f Evidence or history of bleeding diathesis or any hemorrhage or bleeding event >CTCAE grade 3 ≤ 4 weeks prior to randomization.
- 3.29g Non-healing wound, ulcer, or bone fracture.
- 3.29h Renal failure requiring hemo-or peritoneal dialysis.
- 3.29i Dehydration CTCAE (version 4.0) grade ≥ 1 .
- 3.29j Substance abuse, medical, psychological or social conditions that may interfere with the patient's participation in the study or evaluation of the study results.
- 3.29k Known hypersensitivity to any of the study drugs, study drug classes, or excipients in the formulation.
- 3.29l Interstitial lung disease with ongoing signs and symptoms at the time of informed consent.
- 3.29m Persistent proteinuria of CTC Grade 3 or higher (≥ 3.5 g/24 hrs).
- 3.29n Patients unable to swallow oral medications.
- 3.29o Any malabsorption condition.
- 3.29p Unresolved toxicity greater than CTCAE (version 4.0) Grade 1 attributed to any

prior therapy/procedure excluding alopecia and oxaliplatin induced neurotoxicity \leq Grade 2.

- 3.29q Albumin levels <2.5 g/dl.
- 3.29r Any of the following because this study involves an agent that has known genotoxic, mutagenic and teratogenic effects:
- Pregnant women
 - Nursing women
 - Men or women of childbearing potential who are unwilling to employ adequate contraception
- NOTE: Men and women of childbearing potential must agree to use adequate contraception beginning at the signing of the ICF until at least 3 months after the last dose of study drug. The definition of adequate contraception will be based on the judgment of the principal investigator or a designated associate.
- 3.29s Co-morbid systemic illnesses or other severe concurrent disease which, in the judgment of the investigator, would make the patient inappropriate for entry into this study or interfere significantly with the proper assessment of safety and toxicity of the prescribed regimens.
- 3.29t Immunocompromised patients and patients known to be HIV positive and currently receiving antiretroviral therapy. NOTE: Patients known to be HIV positive, but without clinical evidence of an immunocompromised state, are eligible for this trial.
- 3.29u Receiving any other investigational agent which would be considered as a treatment for the primary neoplasm.
- 3.29v Previous or concurrent cancer that is distinct in primary site or histology from colorectal cancer within 3 years prior to randomization EXCEPT for curatively treated cervical cancer in situ, non-melanoma skin cancer and superficial bladder tumors [Ta (Non-invasive tumor), Tis (Carcinoma in situ) and T1 (Tumor invades lamina propria)]. Note: All cancer treatments for cancers that were distinct in a primary site other than colorectal must be completed at least 3 years prior to randomization (i.e., signature date of the informed consent form).
- 3.29w Pleural effusion or ascites that causes respiratory compromise (\geq CTCAE version 4.0 Grade 2 dyspnea).
- 3.29x Concurrent anti-cancer therapy \leq 4 weeks from registration (chemotherapy, radiation therapy, surgery, immunotherapy, biologic therapy, or tumor embolization).
- 3.29y Current use of clobetasol propionate.
- 3.29z Use of any herbal remedy (e.g. St. John's Wort [*Hypericum perforatum*]).

- 3.29aa Patients unable to ambulate or who have amputations or paralysis of any extremity.
- 3.29bb History of contact dermatitis to clobetasol propionate or similarly fluorinated steroids or other steroids with the propionate ester.

4.0 Test Schedule

Tests and procedures	Active Monitoring Phase										
	≤7 days prior to randomization	Cycle 1 ¹³				Cycle 2 ¹³				After week 8: Every 4 weeks until progression (+/- 3 days)	At PD, withdrawal or removal
		Week 1 (Day 1)	Week 2 (Day 8)	Week 3 (Day 15)	Week 4 (Day 22)	Week 1 (Day 1)	Week 2 (Day 8)	Week 3 (Day 15)	Week 4 (Day 22)		
History and exam, weight, ECOG PS ¹² , blood pressure	X	X ¹²	X	X	X	X	X	X	X	X	X
Height	X										
Adverse event assessment ⁸	X		X	X	X	X	X	X	X	X	X
Hematology ^{8, 11} : CBC/ differential, ANC, INR/PTT ^{8, 10}	X	X				X				X	
Chemistry ^{8, 11} : SGOT (AST), alk phos, T. bili, serum creatinine, calcium, glucose, Na, K, SGPT (ALT)	X	X		X ⁷		X ⁷		X ⁷		X	
Albumin	X										
Urine proteinuria or urine protein creatinine ratio	X										
Tumor measurement ⁸ (CT scan of chest, abdomen and pelvis) (MRI if CT is not feasible)	X ¹								X ¹	X ¹	X ^{1,9}
ECG ⁶	X										
Serum pregnancy test	X ²										
Mandatory blood sample (see Section 14.0)	X ^{4,R}	(Day 7) X ^{4,R}	(Day 14) X ^{4,R}	(Day 21) X ^{4,R}		(Day 1) X ^{4,R}		(Day 21) X ^{4,R}			
Patient Medication Diary (Appendix II) ³		X	X	X	X	X	X	X	X	X	
Patient Questionnaire Booklets (Appendices IV, V, VI)	X ⁵		X ^{5,8}			X ^{5,8}	X ^{5,8}		X ^{5,8}		

1. CT scans preferred (MRI if CT is not feasible) of the chest, abdomen and pelvis. Use same imaging throughout the study. Tumor measurements at baseline (≤28 days prior to randomization) and every 8 weeks until progression.
2. For women of childbearing potential only.

3. The diary must begin the day the patient starts taking the medication and must be completed per protocol and returned to the treating institution weekly during Cycles 1 and 2 and every 4 weeks thereafter.
 4. Kits are required for this collection. Samples will be collected for PK analysis of C_{min} of regorafenib, M2 and M5 at the following time points: Cycle 1, days 7, 14 and 21 prior to treatment; Cycle 2, days 1 and 21, prior to treatment. Samples will be collected for research banking at the following time points: Baseline, prior to treatment; Cycle 2, days 1 and 21, prior to treatment. See Section 14.0 for specific instructions.
 5. Patient questionnaires will be completed at baseline (appendices IV and V only), Cycle 1 Day 14, Cycle 2 Day 1, Cycle 2 Day 14 and Cycle 2 Day 28. Cycle 2 Day 14 and Cycle 2 Day 28 patient questionnaire can be sent home with the patient to complete and return at their next clinic visit if needed. Patient questionnaire booklets **must** be used; copies are not acceptable for this submission.
 6. Performed at screening and then as needed.
 7. AST, ALT and total bilirubin will be checked at baseline and every other week during Cycles 1 and 2.
 8. +/- 1 day. Applies to days 1, 8, 15, and 22; includes baseline tests and procedures for Day 1 Cycle 1.
 9. If patient goes off study during Cycle 1 and last CT scan was done >28 days prior, the CT scan must be done.
 10. If a subject is on warfarin with stable PT/INR at baseline, the PT/INR should be assessed on Day 5 (+/- 3 days). If value is above the therapeutic range, the dose should be modified and the assessment should be repeated weekly until it is stable.
 11. Hematology and chemistry tests to be done prior to each cycle.
 12. If baseline history, exam, weight, ECOG PS, and blood pressure were performed ≤ 3 days of Cycle 1 Day 1, they do not need to be repeated for Cycle 1 Day 1.
 13. It is suggested that patients start treatment Tuesday-Friday to avoid PK collection on Sundays.
- R Research funded (see Section 19.0)

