13.0 Treatment/Follow-up Decision at Evaluation of Patient

- 13.1 A patient is deemed *ineligible* if after registration, it is determined that at the time of registration, the patient did not satisfy each and every eligibility criteria for study entry. The patient may continue treatment off-protocol at the discretion of the physician as long as there are no safety concerns, and the patient was properly registered. The patient will go directly to the event-monitoring phase of the study (or off study, if applicable).
- If the patient received treatment, all data up until the point of confirmation of ineligibility must be submitted. Event monitoring will be required per Section 18.0 of the protocol.
 - If the patient never received treatment, on-study material must be submitted. Event monitoring will be required per Section 18.0 of the protocol.
- 13.2 A patient is deemed a major violation, if protocol requirements regarding treatment in cycle 1 of the initial therapy are so severely violated that evaluability for the primary endpoint is questionable. All data up until the point of confirmation of a major violation must be submitted. The patient will go directly to the event-monitoring phase of the study. The patient may continue treatment off-protocol at the discretion of the physician as long as there are no safety concerns, and the patient was properly registered. Event monitoring will be required per Section 18.0 of the protocol.
- 13.3 A patient is deemed a cancel if he/she is removed from the study for any reason before any study treatment is given. On-study material and the End of Active Treatment/Cancel Notification Form must be submitted. No further data submission is necessary.
- 13.4 Patients will continue treatment until progression, unacceptable adverse events, or patient refusal. Treatment will then be discontinued and the patient will go to event monitoring and be followed per Section 18.0.
- 13.5 Patients who are CR, PR, or SD will continue treatment per protocol.
- 13.6 Patients who develop PD while receiving therapy will go to the event-monitoring phase.
- 13.7 Patients who go off protocol treatment for reasons other than PD will go to the event-monitoring phase per Section 18.0.

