16.3 Statement for Primary Endpoint

The primary endpoint is the proportion of patients in each arm who complete 2 cycles of protocol treatment and initiate cycle 3. The proportion will be calculated among evaluable patients separately by arm (Arm A vs. Arm B). Evaluable patients are defined as patients who are eligible, consented, received any protocol treatment. In the CORRECT trial, among patients who were randomized to regorafenib, 45% continued treatment beyond cycle 2. Other than disease progression, majority of patients discontinued regorafenib due to adverse events not associated with progression. It was noted that most adverse events occurred during Cycles 1-2 of the treatment (Grothey A et. al., 2013, Lancet). Assuming 45% of patients would complete 2 cycles of protocol treatment and initiate cycle 3 in the control (standard dose; pooled arms B1 and B2) group, and desiring an improvement to 63% in the experimental (starting low dose) group (pooled arms A1 and A2), a one-sided test with $\alpha = 0.20$ and power of 80% will require a sample size of 110 patients enrolled to both regorafenib arms (A and B). We will enroll 13 additional patients to account for ineligibility, cancellation, major treatment violation, or other reasons. Maximum projected accrual is therefore 123 patients. A Fisher exact test will be used to detect a difference in proportion of patients who complete 2 cycles of protocol treatment and initiate cycle 3 between arms (starting low dose [pooled arm A1 and A2] vs. standard dose [pooled arm B1 and B2]). The proportion of patients who complete 2 cycles of protocol treatment and initiate cycle 3 will be computed by arm with its 95% confidence interval using exact method.

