16.8 Missing Data

Patients with missing data will be excluded from relevant analyses; no imputation of missing data will be performed.

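### No QOL booklet is scheduled once a patient leaves treatment, so the cycle 2 QOL comparison of the dosing arms is conditional on still being treated, and the design's own target rates imply unequal loss

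*Combined protocol and SAP*

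**What the plan says.** Goal 2.24 is to "Compare QOL between treatment arms (regorafenib dosing strategies and pre-emptive vs. reactive PPES strategies"), using the HFS-14, BFI and LASA. Footnote 5 of the test schedule (4.0) sets the collection days: "Patient questionnaires will be completed at baseline (appendices IV and V only), Cycle 1 Day 14, Cycle 2 Day 1, Cycle 2 Day 14", followed by Cycle 2 Day 28. It allows the last two booklets to be taken home and returned at the next visit.

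The booklet row of 4.0 has no mark in the *At PD, withdrawal or removal* column, although that column has an examination and an adverse event assessment. In 18.1 the treatment booklet is due at evaluations during treatment. It has no mark at end of treatment, and no questionnaire is among the event-monitoring forms.

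For patients who stop for progression, adverse events or refusal, 13.4 says: "Treatment will then be discontinued and the patient will go to event monitoring and be followed per Section 18.0". Section 13.7 sends those who leave for other reasons to event monitoring as well. Section 16.8 says: "Patients with missing data will be excluded from relevant analyses; no imputation of missing data will be performed".

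Section 16.46 names the t-test or Wilcoxon test for the HFS-14 and for change in the LASA overall item. It mentions time-dependence for the HFS-14 without naming a model, and the BFI only in the hypothesis.

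For retention, 16.3 plans on "Assuming 45% of patients would complete 2 cycles of protocol treatment and initiate cycle 3 in the control" group and "desiring an improvement to 63% in the experimental (starting low dose) group".

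**The concern.** Whether a patient has a cycle 2 QOL score depends on whether that patient is still on treatment, and staying on treatment is what the dosing strategy is meant to change. Section 1.32 says that many patients discontinue in the first two cycles because of adverse events, so loss of QOL data is plausibly related to QOL itself. If Arm A keeps on treatment patients who would have left under Arm B, the two arms' cycle 2 means come from differently selected groups. A real QOL advantage of the escalating schedule could then be understated. Scores that were never collected cannot be recovered at analysis, so the remedy has to be in the schedule.

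**Working it through.** **1. The planning rates.** Section 16.3 states that "a one-sided test with $\alpha = 0.20$ and power of 80% will require a sample size of 110 patients enrolled to both regorafenib arms", and that "A Fisher exact test will be used to detect a difference in proportion". With 45% against 63%, the normal formula gives (0.8416 × √(2 × 0.54 × 0.46) + 0.8416 × √(0.45 × 0.55 + 0.63 × 0.37))² / 0.18² = 42.7, or 43 per arm. With continuity correction this is 54 per arm (108). Exact one-sided Fisher power is 0.797 at 54 per arm and 0.804 at 55, so 110 reproduces. The 13 extra patients (110 / 0.90, rounded up, is 123) cover ineligibility, cancellation and similar losses. The plan gives no sample size, standard deviation or missing-data rate for QOL.

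**2. Where a stopping patient's booklets end.** A patient who leaves in cycle 1 or 2 has the booklets up to that day. The removal visit adds none, event monitoring adds none, and 16.8 drops the patient from comparisons at later visits. The effect is small at C1D14, grows through C2D1 and C2D14, and is largest at C2D28.

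**3. Upper bound at C2D28.** Suppose everyone who does not start cycle 3 also lacks the C2D28 booklet. With 55 per pooled arm:
- Arm A: 55 × 0.63 = 34.65 booklets, 37% missing.
- Arm B: 55 × 0.45 = 24.75 booklets, 55% missing.
- Total: 59.4 of 110. Gap: 55 − 37 = 18 points.

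**4. Relaxing the bound.** The first scheduled on-study scan is in week 4 of cycle 2, so some patients can give the C2D28 booklet and then leave. Let f be the fraction of those not starting cycle 3 who still return it. Retention is 0.63 + 0.37f in A and 0.45 + 0.55f in B, and the gap is 0.18(1 − f).

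| f | Arm A | Arm B | Gap (points) |
|---|---|---|---|
| 0 | 63% | 45% | 18 |
| 0.25 | 72% | 59% | 13.5 |
| 0.50 | 82% | 73% | 9 |
| 0.75 | 91% | 86% | 4.5 |

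**5. What this could do to the estimate (illustrations; d and ρ are assumed).**

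*Equal stayers.* Stayers average S in both arms and stoppers S − d. The true A − B difference is (S − 0.37d) − (S − 0.55d) = 0.18d. At f = 0 the observed difference is 0, so 0.18d is hidden: 1.8, 3.6 or 5.4 points for d = 10, 20 or 30 on a 0–100 scale. If returned booklets are typical of stoppers, the observed difference is d × [0.55f/(0.45 + 0.55f) − 0.37f/(0.63 + 0.37f)] = 0.106d, 0.152d and 0.172d at f = 0.25, 0.50 and 0.75. The hidden part is then 0.074d, 0.028d and 0.008d.

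*No true difference.* Let ρ be the correlation between QOL and a normally distributed tendency to stay. Stayers' mean exceeds the arm mean by ρφ(z)/p, where p is retention and z the matching normal cut-off. φ(z)/p is 0.599 at p = 0.63 and 0.880 at p = 0.45, so at f = 0 the comparison leans toward Arm B by 0.28ρ SD: 0.08, 0.14 or 0.20 SD for ρ = 0.3, 0.5 or 0.7.

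**6. Precision.** At an assumed two-sided 5% and 80% power, the detectable difference is 2.80 × √(1/n_A + 1/n_B): 0.53 SD at 55 against 55, and 0.74 SD at 34.65 against 24.75.

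**The case against.** The case on the other side has several sound parts.

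- *Early data survive.* Section 1.1 places PPES onset in the first 1–2 weeks, so C1D14 falls in that window, and early leavers remain in the C1D14 and often the C2D1 comparison. A reader might infer that goal 2.24 is answered only in patients who tolerated treatment. The documents do not support that.
- *Poor tolerance often does not mean leaving.* Section 8.3 provides for interruption and dose reduction before discontinuation in many cases, and such patients still have booklets due. Others leave for progression.
- *That booklets stop is inferred.* No sentence says so. Section 8.3 lets the rest of follow-up continue after one kind of discontinuation, and the event-monitoring table lists a QOL-only consent withdrawal form. Neither provides for a booklet, however. Footnote 5, the test schedule and both tables in 18.1 agree in scheduling none. If off-treatment collection was intended, sites are not told.
- *The 18-point gap is a ceiling.* It uses failure to start cycle 3 as a stand-in for a missing booklet, and 63% is a target rather than a forecast. If true retention is equal, the overall gap vanishes, though reasons for leaving may still differ.
- *Consequence is limited.* QOL is secondary and unpowered. PPES and fatigue are graded at each evaluation and compared at grade 3 or 4 under 16.45. An on-treatment QOL question is also legitimate in a tolerability trial, but the plan does not say that this is the question.

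The time-dependence remark in 16.46 could help in part if scores before leaving predict later ones. But it names no model, applies only to the HFS-14, and cannot supply a score from the time of stopping.

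**Conclusion.** The concern holds in limited form. As written, the plan makes the cycle 2 comparisons of the dosing arms conditional on remaining on treatment, mainly at C2D14 and C2D28. The design's rates imply at most 55% against 37% missing at C2D28, and a smaller gap to the extent that patients leaving around the week-8 scan return that booklet. This rests on the 45% and 63% rates and on sites following the schedule literally.

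The size of any bias is not known. Under the equal-stayers assumption it is at most 0.18d points, and d is not in the documents. A reader might infer that the QOL result will be reversed. The equal-stayers calculation can only hide a benefit; a reversal needs further assumptions, such as an assumed ρ, which the documents also do not supply. A reader might equally extend the point to pre-emptive against reactive clobetasol. The plan assumes no retention difference there, so that comparison is affected only if clobetasol changes who stays on treatment. The primary endpoint and the sample size of 110 are untouched. This is an inexpensive improvement worth making.

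**What to change.** 1. **Section 4.0 and 18.1.** Add the questionnaire booklet to the *At PD, withdrawal or removal* column and to *At end of treatment*, for patients stopping before C2D28. State in footnote 5 whether the remaining scheduled booklets continue after treatment stops.
2. **Section 16.46.** Compare the dosing arms in a longitudinal mixed model of all treated patients with any post-baseline booklet, entering off-treatment booklets at their actual time, with a missing-not-at-random sensitivity analysis. Adjust for baseline only where one exists: footnote 5 limits baseline to two of the three appendices. A last-score or worst-score summary would not serve. The last score mixes time points, and the worst score gives patients who stay longer more chances of a bad value, which penalises the arm with better retention.
3. **Reporting.** Give booklet completion by arm, visit and reason for stopping, and label the per-visit t-test or Wilcoxon results as conditional on remaining on treatment.

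The cost is one extra booklet per early stopper at a visit already scheduled, two table edits and one further analysis. Some patients with progression will not complete it. Scores at progression partly reflect disease rather than tolerability, which is why reason for stopping should be shown. One booklet at stopping reduces the problem but does not replace a C2D28 score, so the sensitivity analysis is still needed.
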